3.2 MACE

The primary study objective evaluates whether patient copayment reduction leads to lower risk of MACE at one year. MACE is defined as the composite of all-cause death, recurrent myocardial infarction, and stroke. Follow-up will be censored at time of study withdrawal or last known alive. The time-to-first MACE event up to one year post-discharge will be compared between intervention and control arms. Cumulative incidence rates will be presented as Kaplan-Meier curves and in tables for 30 days, 6 months, and 1 year post-discharge. The primary analysis will be a Cox proportional hazards model accounting for within hospital clustering using robust standard errors and adjustment for selected patient characteristics (Section 8.3.1) which includes a propensity score for intervention. We will use the same propensity score described in section 3.1. Cluster heterogeneity will be quantified using ICCs calculated from unadjusted and adjusted models. We will calculate the ICCs across all hospitals and also by treatment group.

After Steering Committee consensus, the randomization scheme was changed from 1:1 to 2:1 Usual Care vs. Intervention effective November 16, 2015. Randomization schema was added as a covariate for adjustment as shown in Section 8.3.1 and to the propensity model as shown in Section 8.3.2.

4. Secondary Endpoints

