3.1 Non-persistence with antiplatelet therapy at 1 year

The co-primary endpoint of long-term non-persistence will be assessed using patient-reported medication non-persistence. Permanent and temporary discontinuation of a P2Y₁₂ receptor inhibitor will be queried at each follow-up interview. For patients with missing patient-reported medication information, pharmacy fill data will be used to ascertain persistence. Patients who have continued P2Y₁₂ receptor inhibitor use at one year from discharge with less than 30

Statistical Analysis Plan

continuous days of interruption will be considered persistent. We will use the last observation carried forward (LOCF) method for patients who died before one year or had missing 1 year P2Y₁₂ status.

The co-primary objective determines whether patient copayment reduction leads to higher long-term persistence with antiplatelet therapy at one year. The study endpoint for this objective is the proportion of patients at one year who had an interruption ≥ 30 days of P2Y₁₂ receptor inhibitor. The primary analysis will be a logistic regression model with parameters estimated using generalized estimating equations (GEE) to account for within hospital clustering and adjustment for selected patient characteristics (Section 8.3.1) which includes a propensity score for intervention (Section 8.3.2). The propensity score will be estimated using a logistic regression model for intervention group. Categorical variables will be included as sets of indicator variables. Continuous variables will be included assuming a simple linear relationship. Balance of covariates between intervention and usual care arms will be assessed using standardized differences as recommended by Austin [6]. We will assess functional form and possible transformations of the propensity score to be included in the outcome model. Cluster heterogeneity will be quantified using ICCs calculated from unadjusted and adjusted models. We will calculate the ICCs across all hospitals and also by treatment group.

After Steering Committee consensus, the randomization scheme was changed from 1:1 to 2:1 Usual Care vs. Intervention effective November 16, 2015. Randomization schema was added as a covariate for adjustment as shown in Section 8.3.1 and to the propensity model as shown in Section 8.3.2.

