4.7 Safety – Bleeding

Bleeding events will be collected using the Bleeding Academic Research Consortium (BARC) bleeding definition. Additionally, the severity of bleeding will be categorized using the Global Utilization of Streptokinase and t-PA for Occluded Coronary Arteries (GUSTO) definition for severe, moderate, or mild bleeding. We will assess the effect of copayment reduction on bleeding using the same methods as the composite MACE outcome.

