4.9 Components of MACE

We will assess the effect of copayment reduction on each component of MACE using the same methods as the composite MACE outcome.

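### MACE and the other non-fatal endpoints are censored on a vital-status date, so any time known alive but not checked for MI or stroke counts as event-free

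*SAP*

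**What the plan says.** Section 3.2 defines the endpoint: "MACE is defined as the composite of all-cause death, recurrent myocardial infarction, and stroke". The comparison is of time to first event: "The time-to-first MACE event up to one year post-discharge will be compared between intervention and control arms". The censoring rule is "Follow-up will be censored at time of study withdrawal or last known alive", and the model is stated as follows: "The primary analysis will be a Cox proportional hazards model accounting for within hospital clustering using robust standard errors". The SAP gives no other censoring rule for MACE.

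The rule carries over. Section 4.9 says "We will assess the effect of copayment reduction on each component of MACE using the same methods as the composite MACE outcome", and section 4.7 says "We will assess the effect of copayment reduction on bleeding using the same methods as the composite MACE outcome". Sections 4.8, 4.10 and 4.11 do the same for unplanned revascularization, MACE plus revascularization and cardiovascular death.

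Other relevant places:
- Section 2.1 keeps every enrolled patient in the analysis, whether or not follow-up was completed.
- Section 2.4 (missing data) covers operational review and imputation of baseline variables. It says nothing about incomplete event follow-up.
- Section 6.2 plans a matched analysis and a random-intercept analysis of MACE. Neither varies the censoring rule.

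**The concern.** A last-known-alive date suits an analysis of death. For a composite with MI and stroke, a patient is under observation only while someone is finding out about those events. If the alive date is later than that, the patient stays in the risk set, and in the Kaplan-Meier number at risk, as event-free over time that nobody observed. Stand-alone MI, stroke, bleeding and revascularization contain no death component, so the rule suits them least.

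Two consequences are possible. With similar loss in both arms, event rates are understated and some power is lost. With loss that differs by arm, the hazard ratio is biased as well. Differential loss is conceivable because section 2 acknowledges a lack of blinding and one arm receives a financial benefit.

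**Working it through.** **1. The plan's own figures (section 1.4).** Inputs: control 12%, intervention 9.84%, two-sided 0.05, 1:1 allocation, 11,000 patients at 300 sites, ICC 0.01, CV 0.65.

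- Per-arm n without correction: n = [z(α/2)·√(2·p̄·q̄) + z(β)·√(p₁q₁ + p₂q₂)]² / (p₁ − p₂)². This gives 3272 for 80% power and 3743 for 85%.
- Continuity correction: n_c = (n/4)·[1 + √(1 + 4/(n·0.0216))]². This gives 3364 and 3835, so totals of **6728** and **7670**, exactly as stated.
- Design effect: 1 + [(0.65² + 1)·36.67 − 1]·0.01 = 1.512. Effective size is 11,000/1.512 ≈ **7277**, against 7278 stated.
- Power at 7278 is 83.1% with the correction and 84.0% without.

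The sizing reproduces. It does not depend on the censoring rule, so it neither supports nor weakens the point.

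**2. Illustration of the rule.** The SAP gives no loss rate and no split between fatal and non-fatal events, so both are assumed:
- a share f of patients loses event ascertainment at a uniformly distributed time in the year, while vital status stays known to 1 year;
- a share nf of first MACE events is non-fatal, taken as 0.60 to 0.90;
- hazards are constant, λ = −ln(1 − p), and after loss only death, with hazard λ(1 − nf), is seen.

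Observed 1-year rate = (1 − f)·p + f·E, where E is the average over u from 0 to 1 of 1 − exp[−λu − λ(1 − nf)(1 − u)].

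Example for p = 0.12, nf = 0.75, f = 0.10: λ = 0.1278, E = 0.0764, so the rate is 0.90·0.12 + 0.10·0.0764 = 0.1156.

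**Equal loss in both arms** (ranges over nf; power without continuity correction at 7278):

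| f | Control | Intervention | HR | Power |
|---|---|---|---|---|
| 0% | 12.00% | 9.84% | 0.81 | 84.0% |
| 5% | 11.74–11.83% | 9.62–9.70% | 0.81 | 83.1–83.5% |
| 10% | 11.47–11.65% | 9.41–9.55% | 0.81 | 82.2–82.9% |
| 20% | 10.95–11.31% | 8.97–9.27% | 0.81 | 80.3–81.7% |

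First-order check at f = 10%: missed points ≈ 0.10 × 0.5 × (nf × 12%). This is 0.36 for nf = 0.60 and 0.54 for nf = 0.90, close to the table's 0.35 and 0.53.

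**Unequal loss**, with HR = ln(1 − intervention rate)/ln(1 − control rate):

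| Usual care / intervention loss | True HR 1.00 seen as | True HR 0.810 seen as |
|---|---|---|
| 10% / 5% | 1.016–1.024 | 0.823–0.830 |
| 20% / 10% | 1.033–1.051 | 0.837–0.852 |

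If instead the intervention arm loses 10% and usual care 5%, a true HR of 1.00 is seen as the reciprocal, 1/1.024 to 1/1.016, or about 0.98.

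**The case against.** The strongest reply is that the harm needs the alive date to fall later than the last ascertainment of MI and stroke, and the SAP does not show that it does. If every alive date comes from an interview or record that also captures events, the two dates coincide and no time is wrongly credited. That stands, and it is why no size can be derived from the SAP. It does not remove the point, because nothing in the SAP ties the alive date to such contacts.

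A reader might infer more from section 3.1, which says "For patients with missing patient-reported medication information, pharmacy fill data will be used to ascertain persistence": that pharmacy fills push the alive date beyond the last interview. The SAP does not support this. Fills are used there only to determine persistence, and section 1.4 collects pharmacy records on a subset, with a target of 2500 of about 11,000 patients (2500/11,000 ≈ 23%). Voucher use, which section 4.12 shows is tracked, is likewise nowhere said to set vital status.

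It is also fair to object that the loss rates are assumed, and that assuming vital status is known to 1 year for every lost patient gives an upper-end illustration. With equal loss, power stays within the 80 to 85% that section 1.4 states. If the benefit keeps the intervention arm better followed, the bias works against the intervention, so this is not mainly a false-positive risk.

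Finally, simply moving the censoring date for the composite to the last interview would be wrong. Deaths come after a patient's last interview, so some would drop out of MACE. The fix must deal with that.

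**Conclusion.** The point holds as a defect in a stated rule: a vital-status date censors a composite containing MI and stroke, and the separate non-fatal endpoints inherit it. It does not establish that the trial's hazard ratio is biased; the SAP does not show that the dates diverge or that loss differs by arm.

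If they do diverge, the illustration suggests modest effects. Equal loss of 5 to 20% lowers the control rate to about 11.0 to 11.8% and leaves the hazard ratio near 0.81. Loss of 10% against 5% moves a null hazard ratio by about 0.02, in a direction set by which arm loses more. These figures rest on assumed loss, an assumed non-fatal share of 60 to 90%, constant hazards and complete vital status. For cardiovascular death (section 4.11) and all-cause death, last known alive remains a suitable date. The change is worth making because it is cheap and protects a co-primary analysis.

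**What to change.** In section 3.2:

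1. Censor event-free patients at the earliest of withdrawal, the last date through which non-fatal events were ascertained (interview or record review), and 1 year. Apply this to MACE, MACE plus revascularization, MI, stroke, bleeding and unplanned revascularization.
2. Keep last known alive for all-cause and cardiovascular death.
3. State how deaths enter MACE, so that none is lost by default. For example, count a death as a MACE event if it occurs before the next scheduled contact after the last ascertainment, or if records cover the interval to death. Report later deaths in the all-cause death analysis.
4. Keep the present last-known-alive rule as a sensitivity analysis, and report by arm how much time lies between the two dates.

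If the two dates always coincide, a sentence saying so is enough. Otherwise the cost is a short paragraph, one extra date per patient in the analysis data set, and slightly less follow-up time in the composite. The example death rule counts some deaths in a window where survivors are already censored; the sensitivity analysis will show whether that matters.

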4.8 Unplanned Revascularization

We will assess the effect of copayment reduction on unplanned revascularization using the same methods as the composite MACE outcome.

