4.11 Cardiovascular Mortality

We will assess the effect of copayment reduction on cardiovascular mortality using the same methods as the composite MACE outcome.

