8.2.2 Supplementary Table Shells

Table 8: Longitudinal Patterns of P2Y₁₂ use

	Overall (N=patients)	Copayment Intervention (N=patients)	Usual Care (N=patients)
Overall Duration of any P2Y ₁₂			
Duration of initial P2Y ₁₂			
Summed duration of initial P2Y ₁₂			

Statistical Analysis Plan

Table 9a: Kaplan-Meier Cumulative Incidence

Outcome Time (days)*	Overall (N=X patients)			Copayment Intervention (N=X patients)			Usual Care (N=X patients)		
	KM rate (95% CI)	N remaining	N events	KM rate (95% CI)	N remaining	N events	KM rate (95% CI)	N remaining	N events
MACE 30 180 365									
All-cause death 30 180 365									
MI 30 180 365									
Stroke 30 180 365									
BARC 2+ bleed 30 180 365									
BARC 3+ bleed 30 180 365									
GUSTO Moderate/Severe Bleed 30 180 365									
Unplanned Revascularization 30 180 365									
Cardiovascular death 30									

Statistical Analysis Plan

180									
365									
MACE+Unplanned Revascularization									
30									
180									
365									

*Time (days) from discharge

Statistical Analysis Plan

Table 9b: Kaplan-Meier Cumulative Incidence of MACE among Subgroups

Subgroup Time (days)*	Overall (N=X patients)	Copayment Intervention (N=X patients)			Usual Care (N=X patients)		
	N events	KM rate (95% CI)	N remaining	N events	KM rate (95% CI)	N remaining	N events
Age ≥ 65: 30 180 365							
Age < 65: 30 180 365							
Male: 30 180 365							
Female: 30 180 365							
Private Insurance: 30 180 365							
Government Insurance: 30 180 365							
White: 30 180 365							
Non-white: 30							

Statistical Analysis Plan

180 365							
STEMI: 30 180 365							
NSTEMI: 30 180 365							
In-hosp PCI: 30 180 365							
No In-hosp PCI: 30 180 365							

*Time (days) from discharge

Statistical Analysis Plan

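### One minus Kaplan-Meier slightly overstates the cumulative incidence of bleeding, unplanned revascularization, MI, stroke and cardiovascular death, because the SAP makes no provision for death as a competing event

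*SAP*

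**What the plan says.** SAP section 3.2 defines the composite: "MACE is defined as the composite of all-cause death, recurrent myocardial infarction, and stroke". It sets the censoring rule, "Follow-up will be censored at time of study withdrawal or last known alive", and the descriptive estimator, "Cumulative incidence rates will be presented as Kaplan-Meier curves and in tables for 30 days, 6 months, and 1 year post-discharge".

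Four later sections refer back to this method:

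- 4.7, bleeding: "We will assess the effect of copayment reduction on bleeding using the same methods as the composite MACE outcome".
- Section 4.8, on unplanned revascularization, gives the like instruction.
- 4.9, the MACE components, hence MI and stroke: "We will assess the effect of copayment reduction on each component of MACE using the same methods as the composite MACE outcome".
- 4.11, cardiovascular death: "We will assess the effect of copayment reduction on cardiovascular mortality using the same methods as the composite MACE outcome".

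The table shells confirm that the rates, and not only the Cox models, are carried over. Table 3a puts MI, stroke, the BARC and GUSTO bleeds, unplanned revascularization and cardiovascular death under a 12-month cumulative incidence column with confidence intervals. The supplementary shell, "Table 9a: Kaplan-Meier Cumulative Incidence", lists the same outcomes at 30, 180 and 365 days. The SAP mentions no competing risk and no other estimator of cumulative incidence.

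**The concern.** Cumulative incidence by one year is the proportion of patients who have had the event by then. A patient who dies without bleeding cannot bleed later and should stay in the denominator as a patient without the event. Kaplan-Meier with deaths censored instead removes that patient from the risk set and in effect gives the patient the later risk of those still alive. The result exceeds the cumulative incidence whenever a death without the event is followed by events in others.

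The quantity named in the tables and the estimator therefore agree for MACE, all-cause death and MACE plus unplanned revascularization, but not for the other outcomes. At stake are the absolute rates of the safety endpoint and of the components shown beside MACE, which readers will take as patient risks.

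**Working it through.** **Which outcomes are affected**

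| Outcome (SAP section) | Death that competes | Kaplan-Meier gives cumulative incidence? |
|---|---|---|
| MACE (3.2), all-cause death (4.9), MACE plus unplanned revascularization (4.10) | none | yes |
| Bleeding (4.7), unplanned revascularization (4.8) | any death without the event | no, too high |
| MI, stroke (4.9) | death without the event; the size depends on whether fatal events count, which the SAP does not say | no, too high |
| Cardiovascular death (4.11) | non-cardiovascular death only | no, slightly too high |

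**Inputs.** The SAP gives no mortality or bleeding rate and no figure for this bias, so there is nothing of its own to reproduce on the main point. Section 1.4 assumes 12% one-year MACE in the control group, which caps all-cause mortality under the plan's own assumption. The following are assumptions: a one-year Kaplan-Meier bleeding rate K = 6.0%; one-year mortality D = 4%, 6% or 8%; and event and death hazards with the same shape over time.

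**Formula.** Let l = −ln(1 − K) and d = −ln(1 − D). Then

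true cumulative incidence = l/(l + d) × [1 − (1 − K)(1 − D)].

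With K = 0.06, l = 0.0619.

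| D | d | l/(l + d) | 1 − (1 − K)(1 − D) | True | Excess, points | Relative excess |
|---|---|---|---|---|---|---|
| 4% | 0.0408 | 0.6025 | 0.0976 | 5.88% | 0.12 | 2.0% |
| 6% | 0.0619 | 0.5000 | 0.1164 | 5.82% | 0.18 | 3.1% |
| 8% | 0.0834 | 0.4260 | 0.1352 | 5.76% | 0.24 | 4.2% |

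The relative excess is about half the one-year competing mortality.

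**Tied to the plan's 12% MACE.** If half of the MACE hazard is death and half is non-fatal events, the true cumulative incidence of a non-fatal first event is 6.00%. One minus Kaplan-Meier gives 1 − √0.88 = 6.19%.

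**Cardiovascular death.** If it is half of an assumed 6% total mortality, the true value is 3.00% and one minus Kaplan-Meier gives 1 − √0.94 = 3.05%.

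**Timing.** If events mostly precede deaths, the excess shrinks toward zero. If all deaths came first, the true value would be K(1 − D) and the relative excess 1/(1 − D) − 1, that is 4.2% at D = 4% and 8.7% at D = 8%. The 2% to 4% above is one scenario between these limits.

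**Against sampling error.** Assume 11,000 patients split evenly, 5,500 per arm. The 95% half-width for a 6.0% rate is 1.96 × √(0.06 × 0.94/5,500) = 0.63 points. Section 1.4's MACE inputs (ICC 0.01, CV 0.65, 36.67 patients per site) give a design effect of 1 + [(0.65² + 1) × 36.67 − 1] × 0.01 = 1.512. This implies an effective sample size of about 7,277, against 7,278 in the SAP. Applied to bleeding, it widens the half-width to 0.63 × √1.512 = 0.77 points.

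**Difference between arms.** Suppose mortality is 6% in control and 18% lower, 4.92%, in the intervention arm, with K = 6.0% in both. The excess is 0.18 and 0.15 points, so the arms differ by 0.03 points.

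**The case against.** The strongest reply concerns materiality. The excess lies well inside the confidence interval of each rate. Mortality is held down by design: section 2.2 starts from patients who survived the index hospitalization, and section 1.3 excludes those with a life expectancy under one year. Table 9a also names its estimator, and all-cause death is tabulated beside the other outcomes, so a careful reader can see what was done. All of this stands and is why the point is minor. It does not remove the mismatch: Table 3a's column does not name the estimator, and the excess always runs in one direction.

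A second reply is that the SAP nowhere says in words that deaths are censored. That is true. It follows from the stated censoring rule, the Kaplan-Meier label and the absence of any alternative.

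A reader might also infer more than the document supports:

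- **That the MACE rates are wrong.** They are not, since death is part of the composite. The same holds for section 4.10.
- **That the bias distorts the arm comparison because deaths are expected to differ.** The stated hypothesis concerns MACE and sets no effect on death alone. Even granting an 18% reduction in death, the differential is about 0.03 points.
- **That older patients' rates would be worse affected.** Subgroup Tables 3b, 4b and 9b cover MACE and non-persistence only, so no bleeding or component rate by age is planned.
- **That the Cox models are invalid.** Their hazard ratios remain valid as cause-specific hazard ratios.

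**Conclusion.** The point holds as a minor one. For bleeding, unplanned revascularization, MI, stroke and cardiovascular death, the estimator in the SAP does not estimate the quantity that Tables 3a and 9a name, and it errs upward. For a 6.0% Kaplan-Meier bleeding rate the excess is 0.12 to 0.24 points, and it is nearer 0.05 points for cardiovascular death at 3%. These figures rest on an assumed mortality that the SAP does not give, and on event and death hazards that share a time shape. Only the tabulated rates, curves and their intervals for these outcomes change. No hazard ratio, test or co-primary conclusion does.

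**What to change.** In sections 4.7, 4.8, 4.9 (MI and stroke) and 4.11, and in the matching rows of Tables 3a and 9a and any matching curves, estimate cumulative incidence with the Aalen-Johansen estimator. Death is the competing event, or non-cardiovascular death for cardiovascular mortality. State for MI and stroke whether fatal events count as events.

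Keep Kaplan-Meier for MACE, MACE plus unplanned revascularization and all-cause death. Keep the Cox models, and label the hazard ratios for the affected outcomes cause-specific. Retitle Table 9a so that each row names its estimator.

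The cost is SAP wording and a standard SAS option, with no new data. The reported rates for these outcomes become slightly lower.

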ARTEMIS is a prospective cluster-randomized clinical trial that will evaluate whether patient copayment reduction significantly influences antiplatelet selection and long-term adherence. This study will also examine patient outcomes and the overall cost of care after AMI. After IRB approval, sites will be randomized to either the intervention or the control. Randomization will be stratified by annual site AMI volume and proportion of ticagrelor use using medians across potential sites as cut-offs for identifying high vs. low categories. Approximately 11,000 patients with STEMI or NSTEMI will be enrolled at approximately 300 hospitals.

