Patient-reported persistence to antiplatelet therapy will be validated using pharmacy records that will be collected on a subset of the overall study population. The assumed standard deviation of 0.25 (for the proportion of days covered) is based on a recent randomized clinical trial to assess an intervention designed to improve adherence [4]. Assuming 1:1 randomization and a two-sided Type I error rate of 0.05, a sample size calculation based on the two-sample t-test suggests that a total sample size of 1644 patients will yield 90% and a total sample size of 2034 will yield 95% power. A random sample of 2400 patients from the 300 sites randomized with a CV of 0.25 and an ICC of 0.025 would yield a design effect of approximately 1.26. The resulting effective sample size of 2021 patients would yield approximately 95% power to detect a difference of 4% between the patient copayment reduction intervention and control groups. The target sample size of 2500 patients with pharmacy records allows for 4% missing data due to records that are not available.

2. General Considerations for Data Analysis

We will include a detailed flow diagram showing the number of participants' eligible, number of subjects randomized to Copayment Intervention and Usual Care arms, numbers of subjects lost to follow-up or excluded from analyses, and the number of subjects analyzed for the key study endpoints. Additionally, we will describe the number of clinical sites in Copayment Intervention and Usual Care arms including the mean (median, range) for key study elements by site. Key elements will include the following items: descriptions of participants, interventions, objectives, outcomes, and sample size justification; and details about the randomization procedure, factors used to stratify randomization, (lack of) blinding, statistical methods, participant flow, dates of recruitment, baseline data by individuals and by cluster, numbers analyzed, outcomes and estimation, adverse events, and a discussion. These elements are based on the CONSORT statement for cluster randomized studies [5].

After Steering Committee consensus, the randomization scheme was changed from 1:1 to 2:1 Usual Care vs. Intervention effective November 16, 2015. Randomization schema was added below as a covariate for adjustment.

All analyses will be conducted using SAS version 9.4 or higher software. All tests will be two-sided and a p-value of <0.05 will be considered statistically significant.

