Cardiogenic shock (Killip IV on presentation or in-hospital cardiogenic shock)			
Heart failure (Killip II/III on presentation or in-hospital heart failure)			
Cardiac Arrest			
Health Literacy			
Baseline angina frequency			
Cardiac Rehab			
Baseline PHQ2>3			
Baseline EQ5D VAS			
Married			
Employed			
Education (college graduate)			
Baseline financial hardship			
Missed >1 dose of medication in the last month			

Statistical Analysis Plan

Table 3a: Clinical Outcomes by Copayment Intervention

Outcome	Cumulative Incidence at 12 months (95% CI)			Unadjusted		Adjusted	
	Overall (N=)	Copayment Intervention (N=)	Usual Care (N=)	HR (95% CI)	P- value	HR (95% CI)	P- value
MACE							
All-cause death							
MI							
Stroke							
BARC 2+ bleed							
BARC 3+ bleed							
GUSTO Moderate/Severe Bleed							
Unplanned Revascularization							
MACE + unplanned revascularization							
Cardiovascular death							

Statistical Analysis Plan

Table 3b: Subgroup Analysis of MACE by Copayment Intervention

Subgroup	Cumulative Incidence at 12 months (95% CI)			Unadjusted		Adjusted	
	Overall (N=)	Copayment Intervention (N=)	Usual Care (N=)	HR (95% CI)	P-value	HR (95% CI)	P-value
Age							
≥65							
<65							
Sex							
Male							
Female							
Insurance type							
Private							
Non-private							
Race							
White							
Non-white							
MI type							
STEMI							
NSTEMI							
In-hospital PCI							
In-hospital PCI							
No in-hospital PCI							

Statistical Analysis Plan

Table 4a. Medication Non-Persistence by Copayment Intervention

Outcome	Persistence at 12 months			Unadjusted		Adjusted	
	Overall (N=)	Copayment Intervention (N=)	Usual Care (N=)	OR (95% CI)	P-value	OR (95% CI)	P-value
Non-persistence to any P2Y ₁₂ vs. persistence							
Non-persistence or mortality to any P2Y ₁₂ vs. persistence							
Non-persistence to initial P2Y ₁₂ vs. persistence							

Statistical Analysis Plan

Table 4b. Subgroup Analysis of Medication Non-Persistence to Any P2Y₁₂ by Copayment Intervention

Subgroup	Persistence at 12 months			Unadjusted		Adjusted	
	Overall (N=)	Copayment Intervention (N=)	Usual Care (N=)	OR (95% CI)	P-value	OR (95% CI)	P-value
Age							
≥65							
<65							
Sex							
Male							
Female							
Insurance type							
Private							
Non-private							
Race							
White							
Non-white							
MI type							
STEMI							
NSTEMI							
In-hospital PCI							
In-hospital PCI							
No in-hospital PCI							

Statistical Analysis Plan

Table 5. ICCs

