8.3 Appendix: List of Adjustment Variables

8.3.1 Adjustment Variables for Primary Models

Variable	Variable Type
Intervention	Yes/no
Randomization scheme	Categorical (2:1 vs. 1:1 scheme)
Interaction* between intervention and randomization scheme	Categorical
Site MI volume	Categorical (high vs. low)
Site % Ticagrelor use	Categorical (high vs. low)
Age	Continuous
Male gender	Yes/no
Race	Categorical (white vs. nonwhite)
Insurance Payors	Categorical (private vs. non-private)
Region	Categorical (Northeast, West, South, vs. Midwest)
Propensity for intervention	Continuous

*We will test for significant interaction and will drop if the interaction term is not significant.

Statistical Analysis Plan

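### The unadjusted ratios and p-values and the rates by arm ignore the mid-trial change from 1:1 to 2:1 allocation and can be biased if early and late sites differ; the adjusted co-primary models already handle it.

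*SAP*

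**What the plan says.** The unit of randomization is the hospital: "After IRB approval, sites will be randomized to either the intervention or the control". SAP Sections 2, 3.1 and 3.2 all record that "the randomization scheme was changed from 1:1 to 2:1 Usual Care vs. Intervention effective November 16, 2015".

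The plan responds to the change in several places:
- Sections 3.1 and 3.2 handle it in the models: "Randomization schema was added as a covariate for adjustment as shown in Section 8.3.1 and to the propensity model as shown in Section 8.3.2".
- Section 8.3.1 also lists an intervention-by-scheme interaction, with the note "We will test for significant interaction and will drop if the interaction term is not significant".
- Section 6.1 matches patients within scheme and within the site strata.
- Tables 1 and 2b report scheme by arm, and the CONSORT diagrams in Figures 2a and 2b are drawn separately for each scheme.

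The between-arm outputs are laid out differently. The shells "Table 3a: Clinical Outcomes by Copayment Intervention" and "Table 4a. Medication Non-Persistence by Copayment Intervention", with their subgroup versions 3b and 4b, have 12-month rates by arm, an unadjusted ratio with a p-value, and an adjusted ratio with a p-value. Tables 9a and 9b give Kaplan-Meier rates by arm. For the curves, Section 3.2 says "Cumulative incidence rates will be presented as Kaplan-Meier curves and in tables for 30 days, 6 months, and 1 year post-discharge", and the contents list titles Figure 3 as curves by copayment intervention. None of these shells or descriptions mentions stratifying, weighting or splitting by scheme.

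**The concern.** Randomization makes the arms comparable within each scheme. Once 1:1 and 2:1 sites are pooled by arm, the arms differ systematically in their mix of early and late sites. If late-randomized sites have different outcome risk for any reason, the pooled contrast mixes that difference with the intervention effect.

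The outputs concerned cover both co-primary endpoints and bleeding. The primary models yield an odds ratio and a hazard ratio, so these tables and curves are the only planned absolute rates by arm. They are also the natural check on primary models that include a propensity score built from some 50 variables. If scheme is left out of the unadjusted column, a gap between unadjusted and adjusted results could come from the allocation change, from chance imbalance or from the covariate adjustment, and the two columns alone would not show which.

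**Working it through.** **The plan's own figures.** These are needed only for targets and standard errors, and they are not in dispute. The continuity-corrected two-proportion calculation gives 6728 (80% power) and 7670 (85%) for MACE at 12% vs 9.84%, and 5392 (90%) and 4622 (85%) for persistence at 70% vs 74%. All four match Section 1.4. The design effect is 1 + ((CV² + 1)m − 1) × ICC with m = 36.67 and CV = 0.65:
- Persistence, ICC 0.025: 2.279, so 11,000 / 2.279 ≈ 4827 (stated 4827).
- MACE, ICC 0.01: 1.512, so an effective size of 7277 (stated 7278).

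**Share of late-site patients by arm.** Let L be the share of all patients who are at 2:1 sites. The SAP does not give it, so L = 0.25, 0.50 and 0.75 are assumptions. Patient numbers are assumed to follow the allocation ratio within each scheme.
- Intervention: (L/3) / ((1−L)/2 + L/3)
- Usual care: (2L/3) / ((1−L)/2 + 2L/3)

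| L | Intervention | Usual care | Difference (points) |
|---|---|---|---|
| 0.25 | 18.2% | 30.8% | 12.6 |
| 0.50 | 40.0% | 57.1% | 17.1 |
| 0.75 | 66.7% | 80.0% | 13.3 |

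**Bias in the crude difference.** With no true effect in either scheme, the bias is the difference in late-site share times the early/late gap in outcome. The gap is also an assumption. The direction of the bias follows the sign of the gap.

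| L | Non-persistence, 5-point gap | MACE, 2-point gap |
|---|---|---|
| 0.25 | 0.126 × 5 = 0.63 points | 0.126 × 2 = 0.25 points |
| 0.50 | 0.171 × 5 = 0.86 points | 0.171 × 2 = 0.34 points |
| 0.75 | 0.133 × 5 = 0.67 points | 0.133 × 2 = 0.27 points |

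That is 16% to 21% of the 4-point persistence target, and 12% to 16% of the MACE target of 12 − 9.84 = 2.16 points.

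**Effect on the unadjusted p-value.** The standard errors use the effective sizes 4827 and 7278, risks of 0.30 and 0.12, and the resulting overall allocation. They are 1.32 to 1.36 points for non-persistence and 0.76 to 0.79 points for MACE. The false-positive rate is Φ(−1.96 + bias/SE) + Φ(−1.96 − bias/SE). It rises from 5% to about 8–10% for non-persistence and about 6–7% for MACE in the scenarios above.

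**Ratio scale.** With half the patients at each type of site, early MACE risk 12% and no true effect, the pooled risk ratio is 1.039 if late-site risk is 20% lower and 0.963 if it is 25% higher. The design target is 0.82. Stratifying by scheme, or standardizing both arms to a common scheme mix, returns exactly 1.00.

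**The case against.** The strongest reply is that nothing inferential depends on these columns. Sections 3.1 and 3.2 define the primary analyses as the adjusted models, which contain scheme. The matched analysis works within scheme, the random-intercept analyses keep the same adjustment, and the secondary endpoints reuse it. Each unadjusted ratio in Tables 3a to 4b sits beside the adjusted one, and Tables 1 and 2b let a reader see the scheme imbalance. This stands. It limits the point to secondary and descriptive outputs, and it rules out saying that a gap between the two columns could not be interpreted at all.

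Two premises are inferred. The SAP does not define unadjusted; that it omits scheme is read from the label and from Section 8.3.1, where scheme appears only among the adjustment variables. Figure 3 is known only by its title, so its layout cannot be checked.

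A reader might go further and infer that early and late sites do confound these results. The SAP reports no early/late difference, so only the possibility is established. Scheme is also fixed when a site is randomized, not when a patient enrols, so calendar time may differ less between schemes than the labels early and late suggest. A 10-point gap in non-persistence would push the false-positive rate to 16–25%, but that case is extreme against the SAP's own ICC. Between-site variance is 0.025 × 0.30 × 0.70 = 0.00525, and a 10-point gap alone would take L(1−L) × 0.01 of it: 36% at L = 0.25 or 0.75, and 48% at L = 0.50.

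The reply that unadjusted results are merely descriptive does not fully hold. The shells attach p-values, and Section 2 declares any p-value below 0.05 statistically significant.

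**Conclusion.** The point holds for the unadjusted ratios and p-values in Tables 3a, 3b, 4a and 4b and for the rates by arm in those tables and in Tables 9a and 9b. Judging by its title, it holds for Figure 3 too. The imbalance in late sites is built in for any mix of the two schemes. The bias that follows is conditional and modest: under the assumed scheme mixes and gaps it reaches at most about a fifth of the target difference for non-persistence and a sixth for MACE, and it is zero if early and late sites have the same risk.

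It would be wrong to conclude that the allocation change undermines the co-primary comparisons. Those models carry scheme, and the matched analysis respects it. This is a weakness in the supporting and absolute-effect reporting, worth correcting because the correction is cheap.

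**What to change.** In Sections 3.1 and 3.2 and the shells for Tables 3a, 3b, 4a and 4b, make the minimal between-arm comparison respect the design, and attach the p-value to that model:
- **Time-to-event outcomes:** a Cox model stratified by randomization scheme, with hospital-robust standard errors.
- **Non-persistence:** GEE logistic regression with intervention plus scheme.

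The two site stratification factors (AMI volume and ticagrelor use) may be added, but scheme alone addresses this point.

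Keep the crude pooled counts, rates and curves, labelled as descriptive and without a between-arm p-value. For the co-primary endpoints, add 12-month rates and, for MACE, Kaplan-Meier curves, either separately for 1:1 and 2:1 sites or standardized to the overall scheme mix. State in the SAP what unadjusted means.

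The cost is some SAP wording, a few lines of code using a variable already needed for the primary models, and a few extra rows or panels. Standardized rates will not equal raw events divided by N, which is why the crude counts should stay beside them.
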